15.3.3. Serious Adverse Events

Any SAE experienced by the subject between the time of the signing of the ICF and the subject's final clinic visit (including the SFU Visit) is to be recorded on an SAE form, regardless of the severity of the event or its relationship to study treatment. SAEs must be reported to Biogen within 24 hours as described in Section 15.3.4. Follow-up information regarding an SAE also must be reported within 24 hours.

Subjects will be followed for all SAEs until the subject's final clinic visit (including the SFU Visit). Thereafter, the event should be reported to Biogen only if the Investigator considers the SAE to be related to study treatment.

Any SAE that is ongoing when the subject completes or discontinues the study will be followed by the Investigator until the event has resolved, stabilized, or returned to baseline status.

15.3.4. Immediate Reporting of Serious Adverse Events

In order to adhere to all applicable laws and regulations for reporting an SAE, the study site must formally notify the Sponsor within 24 hours of the site staff becoming aware of the SAE. It is the Investigator's responsibility to ensure that the SAE reporting information and procedures are used and followed appropriately.

CONFIDENTIAL

The information contained herein may not be used, disclosed, or published without the written consent of Biogen MA Inc.

Reporting Information for SAEs

A report **must be submitted** to the Sponsor regardless of the following:

- Whether or not the subject has undergone study-related procedures
- Whether or not the subject has received study treatment
- The severity of the event
- The relationship of the event to study treatment

To report initial or follow-up information on an SAE, refer to the Study Reference Manual's Official Study Contact List for complete contact information.

15.3.4.1. Deaths

Death is an outcome of an event. The event that resulted in death should be recorded on the appropriate CRF. All causes of death must be reported as SAEs within 24 hours of the site becoming aware of the event. The Investigator should make every effort to obtain and send death certificates and autopsy reports to Biogen. The term death should be reported as an SAE only if the cause of death is not known and cannot be determined.

15.3.5. Suspected Unexpected Serious Adverse Reactions

Suspected unexpected serious adverse reactions (SUSARs) are SAEs that are unexpected and judged by the Investigator or the Sponsor to be related to the study treatment administered.

Appropriate Sponsor personnel will unblind SUSARs for the purpose of regulatory reporting. The Sponsor will submit SUSARs (in blinded or unblinded fashion) to regulatory agencies according to local law. The Sponsor will submit SUSARs to Investigators in a blinded fashion.

15.4. Procedures for Handling Special Situations

15.4.1. Pregnancy

Subjects should not become pregnant or impregnate their partners during the study and for at least 30 days after their last dose of study treatment. If a female subject becomes pregnant, study treatment must be discontinued *immediately*.

The Investigator must report a pregnancy occurring in a female subject or the partner of a male subject by transmitting the appropriate form to the Sponsor within 24 hours of the site staff becoming aware of the pregnancy. Refer to the Study Reference Manual's Official Study Contact List for complete contact information. The Investigator or site staff must report the outcome of the pregnancy to the Sponsor. A pregnancy is not considered an AE and should not be recorded on the AE CRF.

CONFIDENTIAL

The information contained herein may not be used, disclosed, or published without the written consent of Biogen MA Inc.

Congenital abnormalities and birth defects in the offspring of male or female subjects should be reported as an SAE if conception occurred during the study treatment period.

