Protocol Activity	Day 1 ¹	Week 1/ Day 8 ²	Week 2/ Day 15 ^{1,2}	Week 4/ Day 29 ²	Week 6/ Day 43 ^{1,2}	Week 8/ Day 57 ²	Week 10/ Day 71 ²	Week 12/ Day 85 ^{1,2} /ET ³	14 Days After Last Dose ²	
Vital Signs (temperature, supine blood pressure, pulse rate, respiratory rate) ⁶	X	X	X	X	X	X	X	X		
Laboratory Tests										
Urine Drug and Alcohol Test ⁶	X		X		X			X		
Urine Pregnancy Test ^{6, 11}	X			X		X		X	X	
Clinical Safety Laboratory Tests (hematology, blood chemistry, and urinalysis) ⁶	X	X	X	X		X		X	X	
Antipsychotic Blood Sampling	X							X		
Subject/Informant-Reported Outcomes										
Assessments										
MCCB ¹⁵	X		X		X			X		

CONFIDENTIAL

The information contained herein may not be used, disclosed, or published without the written consent of Biogen MA Inc.

Study Phase:	Baseline	Treatment								SFU
Protocol Activity	Day 1 ¹	Week 1/ Day 8 ²	Week 2/ Day 15 ^{1,2}	Week 4/ Day 29 ²	Week 6/ Day 43 ^{1,2}	Week 8/ Day 57 ²	Week 10/ Day 71 ²	Week 12/ Day 85 ^{1,2} /ET ³	14 Days After Last Dose ²	
SCI-PANSS ^{15, 16}	X		X		X			X		
UPSA-Bi ¹⁵	X							X		
SCoRS ^{15, 16}	X							X		
CGI-S ^{15, 17}	X				X			X		
CGI-I ^{15, 17}					X			X		
Dispense Study Treatment ¹⁸	X	X	X	X	X	X	X			
Monitor Dosing Compliance	X	X	X	X	X	X	X	X		
Study Treatment Administration	Oral dosing BID from Day 1 through Day 85-----									
Adverse Event Recording	X -----									
Serious Adverse Event Reporting	X -----									
Concomitant Therapy and Procedures Recording ⁶	X -----									

AE = adverse event; [REDACTED]; CGI-I = Clinical Global Impression–Improvement; CGI-S = Clinical Global Impression–Severity; C-SSRS = Columbia Suicide Severity Rating Scale; ECG = electrocardiogram; [REDACTED]; ET = Early Termination; h = hours; [REDACTED]; MCCB = MATRICS Consensus Cognitive Battery; PK = pharmacokinetic; SAE = serious adverse event; SARA = Scale for the Assessment and Rating of Ataxia; SCI-PANSS = Structured Clinical Interview for Positive and Negative Syndrome Scale; SCoRS = Schizophrenia Cognition Rating Scale; SFU = Safety Follow-Up; [REDACTED]; UPSA-Bi = UCSD (University of California, San Diego) Performance-Based Skills Assessment – Brief, international version.

CONFIDENTIAL

The information contained herein may not be used, disclosed, or published without the written consent of Biogen MA Inc.

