15.1.2. Serious Adverse Event

An SAE is any untoward medical occurrence that at any dose:

- Results in death
- In the view of the Investigator, places the subject at immediate risk of death (a life-threatening event); however, this does not include an event that, had it occurred in a more severe form, might have caused death
- Requires inpatient hospitalization or prolongation of existing hospitalization

CONFIDENTIAL

The information contained herein may not be used, disclosed, or published without the written consent of
Biogen MA Inc.

- Results in persistent or significant disability/incapacity
- Results in a congenital anomaly/birth defect
- Is a medically important event

A medically important event is an AE that, in the opinion of the Investigator, may jeopardize the subject or may require intervention to prevent one of the other outcomes listed in the definition above. (Examples of such medical events include allergic bronchospasm requiring intensive treatment in an emergency room or convulsions occurring at home that do not require an inpatient hospitalization.)

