15.5. Contraception Requirements

All women of childbearing potential and all men must practice highly effective contraception during the study and for at least 30 days after their last dose of study treatment. In addition, subjects should not donate sperm or eggs for the duration of the study and for at least 3 months after their last dose of study treatment.

For the purposes of this study, women who do not meet one of the following criteria listed below are considered to be physiologically capable of becoming pregnant and are, therefore, defined as women of childbearing potential:

CONFIDENTIAL

The information contained herein may not be used, disclosed, or published without the written consent of Biogen MA Inc.

- Postmenopausal
 - 12 months of natural (spontaneous) amenorrhea without an alternative medical cause and a serum follicle-stimulating hormone level >40 mIU/mL
 - 6 weeks after surgical bilateral oophorectomy with or without hysterectomy
- Posthysterectomy
- Female surgical sterilization (e.g., bilateral tubal ligation)

For the purposes of the study, highly effective contraception is defined as use of 1 of the following:

For females:

- Established use of oral, intravaginal, or transdermal combined (estrogen and progestogen containing) hormonal methods of contraception associated with the inhibition of ovulation.
- Established use of oral, injected, or implanted hormonal methods of contraception that contain progestogen alone associated with the inhibition of ovulation.
- Placement of an intrauterine device or intrauterine system.
- Barrier methods of contraception with use of a spermicide: condom or occlusive cap (diaphragm or cervical/vault caps) with spermicidal foam/gel/film/cream suppository. The use of barrier contraceptives should always be supplemented with the use of a spermicide.
- Sex with a male who has undergone surgical sterilization (with the appropriate postvasectomy documentation of the absence of sperm in the ejaculate).

For males:

- The use of condoms with spermicide.
- Sex with a woman who uses the methods described for females if she is of childbearing potential.
- Male surgical sterilization (with the appropriate postvasectomy documentation of the absence of sperm in the ejaculate).

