15.6. Safety Responsibilities

15.6.1. The Investigator

The Investigator's responsibilities include the following:

- Monitor and record all AEs, including SAEs, on the CRF regardless of the severity or relationship to study treatment.
- Determine the seriousness, relationship, and severity of each event.
- Determine the onset and resolution dates of each event.
- Monitor and record all pregnancies in female subjects and follow up on the outcome of all pregnancies.
- Complete an SAE form for each SAE and fax or email it to the Sponsor within 24 hours of the site staff becoming aware of the event.
- Pursue SAE follow-up information actively and persistently. Follow-up information must be reported to the Sponsor within 24 hours of the site staff becoming aware of new information.
- Ensure all AE and SAE reports are supported by documentation in the subjects' medical records.
- Pursue AE follow-up information, if possible, until the event has resolved or become stable. Record AE follow-up information, including resolution, on the CRF, as applicable.
- Report SAEs to local ethics committees, as required by local law.

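### The birth-defect SAE sentence in Protocol 15.4.1 is tied to conception during treatment, which is narrower than the 30-day post-dose risk window in the same section, so SAE classification and 24-hour reporting are not assured for some exposed or at-risk pregnancies

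*Protocol*

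**What the plan says.** Section 15.4.1 (Pregnancy) opens with a risk window: subjects should not become pregnant or "impregnate their partners during the study and for at least 30 days after their last dose of study treatment". It requires a pregnancy in a female subject or in a male subject's partner to be notified to the Sponsor within 24 hours. It also requires the outcome to be reported, with no limit on the date of conception and no stated deadline. It closes with the rule on offspring: congenital abnormalities and birth defects "should be reported as an SAE if conception occurred during the study treatment period".

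Three other places bear on this:

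- Section 15.1.2 includes "Results in a congenital anomaly/birth defect" among the SAE criteria and sets no condition on conception.
- Section 15.3.3 has SAEs recorded from consent to the final clinic visit, including the safety follow-up visit. "Thereafter, the event should be reported to Biogen only if the Investigator considers the SAE to be related to study treatment".
- Section 15.6.1 gives the Investigator the duty to "Monitor and record all pregnancies in female subjects and follow up on the outcome of all pregnancies".

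The dosing period is given in Table 4 (Section 5): "Oral dosing BID from Day 1 through Day 85".

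**The concern.** Section 15.4.1 contains both a window in which it regards conception as hazardous and a rule for when a resulting birth defect is an SAE, and the second is shorter than the first. The SAE rule also turns on the date of conception and not on exposure, so a fetus conceived just before the first dose and exposed afterwards is not named.

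The general SAE sections do not plainly close the gap. The recording duty in 15.3.3 is framed around events in the subject. A birth defect affects the offspring, who may be the child of a partner who was never enrolled. The last sentence of 15.4.1 is the only one that speaks expressly of offspring, so a site is likely to follow it.

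What is at stake is how fast and under what label such a case reaches the Sponsor. About 300 subjects had been exposed to BIIB104 when the protocol was written (Section 4), so one birth defect after exposure could be an important signal. Its handling should not depend on which passage the site reads.

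**Working it through.** The documents give no figure to reproduce. The check compares the passages and counts days. It takes the study treatment period, which 15.4.1 does not define, to run from the first to the last dose, and it assumes a subject who completes dosing.

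**Inputs**
- Dosing: Day 1 to Day 85 (Table 4).
- Pregnancy avoidance: "for at least 30 days after their last dose of study treatment" (15.4.1; Section 15.5 gives the same minimum for contraception).
- Safety follow-up visit: 14 days after the last dose (Table 4, Section 10.1), with a visit window of ±3 days (Table 4, footnote 2).
- Urine pregnancy tests: Day 1, Weeks 4, 8 and 12, and safety follow-up (Table 4).

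**1. Post-dose conceptions**
- Risk window from Day 1: 85 + 30 = 115 days.
- Covered by the SAE sentence: 85 days. Not covered: 30 days.
- Share not covered: 30 / 115 = 26%.

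**2. Part of the 30 days after the final scheduled visit**
- 30 − 14 = 16 days.
- With the visit 11 to 17 days after the last dose: 30 − 17 = 13 to 30 − 11 = 19 days.

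If the study treatment period were stretched to include safety follow-up, these 16 days (13 to 19) would still be uncovered.

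**3. Conceptions before the first dose**
- Next scheduled test after Day 1: Week 4, Day 29.
- Possible exposure before that test: 29 − 1 = 28 days, or 25 to 31 with the visit window.
- This is an upper range for female subjects, because Section 14.2.1 requires an earlier test if a menstrual cycle is missed or pregnancy is suspected. Partners of male subjects have no scheduled test.

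**4. What happens to a birth defect in either group**
- It meets a criterion in 15.1.2, so it can be classed as an SAE.
- The sentence in 15.4.1 that would make it one expressly does not apply.
- A birth will normally fall after the final clinic visit, which comes two weeks after the last dose. A subject with confirmed pregnancy is also withdrawn under 14.2.1.
- After that visit, 15.3.3 takes only SAEs judged related. Section 15.2.2 counts the absence of a plausible time relation as pointing to not related, so a conception outside treatment may invite that answer.
- If the Investigator answers not related, the case reaches the Sponsor as a pregnancy outcome without a stated deadline, and not as an SAE on the 24-hour clock of 15.3.4.

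**The case against.** The strongest reply is that the sentence says *if*, not *only if*. It can be read as naming one group that is always reported, leaving 15.1.2 in force for every other birth defect. Pregnancies in subjects and partners must be notified within 24 hours and their outcomes reported whatever the conception date, so the Sponsor has the information. Section 15.3.5 lets either the Investigator or the Sponsor judge relatedness for a SUSAR. Much of this stands. A reader might infer that these birth defects are excluded from SAE status, go unreported or escape SUSAR assessment, and the documents do not support that. What remains is narrower: classification and timing are not assured when the Investigator judges the event unrelated after the final visit.

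On conception before dosing, the safeguards are substantial. Pregnant women and men with pregnant partners are excluded (8.2), there is a serum test at screening, and a negative test is required before dosing (14.2.1). The route needs contraceptive failure and a conception too recent to detect, so it is the minor part of the point.

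The 26% is a share of calendar days, not of pregnancies or missed defects. That is right, and it should be read only as the size of the mismatch.

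Two further inferences are tempting and do not hold:

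- Section 15.5 says "subjects should not donate sperm or eggs for the duration of the study and for at least 3 months" after the last dose, and one might set this against the 30 days as a contradiction or as a wider yardstick for the SAE rule. Gamete donation is a different act with a different recipient, and the two limits can coexist.
- Section 15.6.1 names only female subjects when it speaks of recording pregnancies. One might infer that partner pregnancies are unmonitored, but the same sentence covers the outcomes of all pregnancies, and 15.4.1 expressly includes partners.

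**Conclusion.** The point holds as an internal mismatch in a safety-reporting rule. Section 15.4.1 treats 30 days after the last dose as at risk, but its only sentence on offspring stops at the end of treatment. This leaves 30 of about 115 days outside it, plus the rare exposed conception before Day 1. The post-dose group is the firmer part, because both statements stand in one section.

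The consequence is limited to uncertain SAE classification and 24-hour reporting. It rests on two assumptions: that the study treatment period means first to last dose, and that sites follow the specific sentence over the general criterion in 15.1.2. Few cases are expected. Sample size, power and the efficacy analysis are untouched. The change is still worth making, because a single case could matter and the remedy is a matter of wording.

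**What to change.** In the last sentence of 15.4.1, replace the conception condition with: *if the fetus was exposed to study treatment, or if conception occurred between the first dose and the end of the post-dose pregnancy-avoidance window stated in this section*. This uses the protocol's own window, without changing its length, and brings the sentence into line with 15.1.2.

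Add one sentence stating that such events are reported as SAEs even when they become known after the final clinic visit, and refer to it from 15.3.3 so that the relatedness condition there does not override it.

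The cost is two sentences, a cross-reference and matching text in the site safety instructions, which could go into the next amendment. No visit, test or data field is added.

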15.4.2. Overdose

An overdose is any dose of study treatment administered to a subject or taken by a subject that exceeds the dose assigned to the subject according to the protocol. Overdoses are not considered AEs and should not be recorded as an AE on the CRF; however, all overdoses must be recorded on an Overdose form and transmitted to the Sponsor within 24 hours of the site becoming aware of the overdose. An overdose must be reported to Biogen even if the overdose does not result in an AE. If an overdose results in an AE, the AE must be recorded. If an overdose results in an SAE, both the SAE and Overdose forms must be completed and transmitted to the Sponsor. All study treatment-related dosing information must be recorded on the dosing CRF.

15.4.3. Medical Emergency

In a medical emergency requiring immediate attention, site staff will apply appropriate medical intervention, according to current standards of care. The Investigator (or designee) should contact the Sponsor's Medical Monitor. Refer to the Study Reference Manual for contact information.

15.4.3.1. Unblinding for Medical Emergency

In a medical emergency when knowledge of the subject's treatment assignment may influence the subject's clinical care, the Investigator may access the subject's treatment assignment by IRT. The Investigator must document the reasons for unblinding in the subject's source documents.

The Investigator is strongly advised not to divulge the subject's treatment assignment to any individual not directly involved in managing the medical emergency, or to personnel involved with the analysis and conduct of the study. The Investigator can contact the Sponsor to discuss such situations but such a discussion should not delay management of the medical emergency.

15.5. Contraception Requirements

All women of childbearing potential and all men must practice highly effective contraception during the study and for at least 30 days after their last dose of study treatment. In addition, subjects should not donate sperm or eggs for the duration of the study and for at least 3 months after their last dose of study treatment.

For the purposes of this study, women who do not meet one of the following criteria listed below are considered to be physiologically capable of becoming pregnant and are, therefore, defined as women of childbearing potential:

CONFIDENTIAL

The information contained herein may not be used, disclosed, or published without the written consent of Biogen MA Inc.

- Postmenopausal
 - 12 months of natural (spontaneous) amenorrhea without an alternative medical cause and a serum follicle-stimulating hormone level >40 mIU/mL
 - 6 weeks after surgical bilateral oophorectomy with or without hysterectomy
- Posthysterectomy
- Female surgical sterilization (e.g., bilateral tubal ligation)

For the purposes of the study, highly effective contraception is defined as use of 1 of the following:

For females:

- Established use of oral, intravaginal, or transdermal combined (estrogen and progestogen containing) hormonal methods of contraception associated with the inhibition of ovulation.
- Established use of oral, injected, or implanted hormonal methods of contraception that contain progestogen alone associated with the inhibition of ovulation.
- Placement of an intrauterine device or intrauterine system.
- Barrier methods of contraception with use of a spermicide: condom or occlusive cap (diaphragm or cervical/vault caps) with spermicidal foam/gel/film/cream suppository. The use of barrier contraceptives should always be supplemented with the use of a spermicide.
- Sex with a male who has undergone surgical sterilization (with the appropriate postvasectomy documentation of the absence of sperm in the ejaculate).

For males:

- The use of condoms with spermicide.
- Sex with a woman who uses the methods described for females if she is of childbearing potential.
- Male surgical sterilization (with the appropriate postvasectomy documentation of the absence of sperm in the ejaculate).

True abstinence, when this is consistent with the preferred and usual lifestyle of the subject, can be considered an acceptable method of contraception based on the evaluation of the Investigator who should also take into consideration the duration of the clinical trial. Periodic abstinence (e.g., calendar, ovulation, symptothermal, postovulation methods) and withdrawal are not considered acceptable methods of contraception.

Pregnancy reporting is described in Section 15.4.1.

CONFIDENTIAL

The information contained herein may not be used, disclosed, or published without the written consent of
Biogen MA Inc.

15.6. Safety Responsibilities

15.6.1. The Investigator

The Investigator's responsibilities include the following:

- Monitor and record all AEs, including SAEs, on the CRF regardless of the severity or relationship to study treatment.
- Determine the seriousness, relationship, and severity of each event.
- Determine the onset and resolution dates of each event.
- Monitor and record all pregnancies in female subjects and follow up on the outcome of all pregnancies.
- Complete an SAE form for each SAE and fax or email it to the Sponsor within 24 hours of the site staff becoming aware of the event.
- Pursue SAE follow-up information actively and persistently. Follow-up information must be reported to the Sponsor within 24 hours of the site staff becoming aware of new information.
- Ensure all AE and SAE reports are supported by documentation in the subjects' medical records.
- Pursue AE follow-up information, if possible, until the event has resolved or become stable. Record AE follow-up information, including resolution, on the CRF, as applicable.
- Report SAEs to local ethics committees, as required by local law.

